3. SUBJECT INFORMATION

3.1. Demographics and Baseline Characteristics

All demographics and baseline characteristic variables will be summarized for the all-treated population by disease type and study cohorts.

No formal statistical hypothesis testing is planned.

- Demographic and baseline characteristics data, including age (continuous and grouped as <65, or ≥65 years), sex, race, ethnicity, weight, height, and ECOG performance status will be summarized.
- Disease characteristics at baseline including time from initial diagnosis to first dose, lymphoma-related symptoms, lactic acid dehydrogenase (LDH), number of lines of prior therapies (continuous and grouped as 1 and 2 to 4 and >4) and lymphocyte count (at baseline).
- Chemistry: creatinine, AST, ALT, total bilirubin, lipase and amylase
- Hematology: hemoglobin, white blood cell, absolute neutrophils, absolute lymphocyte count, and platelet count
- Beta2-microglobulin, serum immunoglobulin levels (IgG, IgM, IgA). For continuous variables, mean, standard deviation, median, minimum, and maximum will be provided. For categorical variables, the number and percentage of subjects in each category will be summarized.

3.2. Disposition Information

Disposition will be summarized for the all-treated population by disease type and study cohorts, including the number and percentage of subjects who are treated and discontinued treatment as well as their reason for discontinuation. Similarly, number of subjects undergoing and discontinuing the study as well as their reasons for study discontinuation will be summarized.

3.3. Medical History

Abnormal medical history findings reported by the investigator will be summarized by body system.

3.4. Extent of Exposure

Extent of exposure for ibrutinib will be summarized for the safety population by disease type and study cohorts. Descriptive statistics (n, mean, standard deviation, median, and range) will be provided for total number of cycles, treatment duration (the interval between date of first dose and date of last dose), and ibrutinib dosing information including total dose received (the sum of administered doses), dose intensity (the ratio of total dose and treatment duration).

Dose reduction for ibrutinib is defined as administered planned lower dose level. There is a one applicable dose level reduction for CLL/SLL cohort: 280 mg/day (level 1 reduction). There are two applicable dose level reductions in FL, DLBCL or Richter syndrome disease cohorts: 420 mg/day (level 1 reduction) or 280 mg/day (level 2 reduction). Dose reduction information will be summarized for the number of subjects with any dose reduction (at least 1 reported dose reduction), as well as the frequency and reason of dose reduction. Number and percentage of subjects with cycle delays will also be presented.

Dose interruption for ibrutinib is defined as missing/skipped dose for ≥ 7 day. The consecutive days of dose interruption are considered as 1 dose interruption. The number and percentage of subjects with dose reduction and dose interruption will be summarized. In addition, subjects with dose modifications (i.e., reductions or interruptions) and reasons for dose modifications will be summarized.

Extent of exposure for nivolumab will be summarized for the safety population by disease type and study cohorts. Descriptive statistics (n, mean, standard deviation, median, and range) will be provided for total number of infusion, infusion duration (the interval between the start time of infusion and the end time of infusion), infusion rate interruption duration (the interval between the start time of infusion interruption and the end time of infusion interruption), and nivolumab dosing information including, total dose administered/received (the sum of actual dose administered), total number of infusions interrupted, total number of infusions skipped, total number of infusions discontinued and total number of infusion rate reductions, interval between 2 consecutive infusions of nivolumab which is defined as end date of prior cycle to first day of following cycle.

Dose modification is defined as at least 1 dose skipped or events occurred during infusion. The frequency and reason of dose skipped or events occurred during infusion will be summarized.

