3.3.3. Dose Expansion - Part B (Recommended Phase 2 Dose)

The dose for the expansion part of this study (Part B) will be determined based on either:

- The highest planned dose (ibrutinib 560 mg daily + nivolumab 3 mg/kg every 2 weeks) in the dose optimization schedule
- A lower dose determined by the SET following a review of all available safety and efficacy data from the dose optimization part of the study (Part A)

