4.1.1. Additional Inclusion Criteria for Part A: Dose Optimization Cohorts

10. Histologically confirmed and documented B-NHL (FL and DLBCL) or CLL/SLL (deletion 17p or deletion 11q as determined by FISH analysis) as conducted by the local lab.
11. Relapsed or refractory disease after at least 1 but not more than 4 lines of prior, systemic therapy.
12. Measurable disease defined as:
 - **B-NHL:** At least 1 measurable site of disease according to the Lugano Classification (see Attachment 6.2). The site of disease must be greater than 1.5 cm in the long axis regardless of short axis measurement or greater than 1.0 cm in the short axis regardless of long axis measurement, and clearly measurable in 2 perpendicular dimensions
 - **CLL:** $\geq 5,000$ leukemia cells/ μL

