6.4.1. Ibrutinib Dose Modifications

Dose reduction levels for ibrutinib, if required in Section 6.4.3, are listed in Table 7.

Table 7: Dose Reduction for Ibrutinib

| Ibrutinib Dose | 420 mg | 560 mg |
|----------------|--------|--------|
| Dose Level -1 | 280 mg | 420 mg |
| Dose Level -2 | NA | 280 mg |

Ibrutinib dose reductions below 280 mg per day are not permitted and may require discontinuation of study therapy after consultation with the Sponsor. Dose escalations of ibrutinib to the previous higher dose may be considered after consultation with the Sponsor.

In Part A, intra-patient dose escalation may be requested by the investigator and discussed with the medical monitor once a subsequent higher combination dose has been declared acceptable by the SET for subjects who (1) have received at least 4 cycles of combination treatment at the assigned dose level, and (2) have not experienced a DLT or therapy-related SAE. Subjects whose dose has been escalated will not be considered for the safety evaluation in the subsequent dose level and the determination of the RP2D.

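### SAP 3.4 labels ibrutinib dose-reduction levels by disease, but the protocol sets them by starting dose, so levels can be wrong or undefined for Part A subjects in the exposure tables.

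*SAP*

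**What the plan says.** SAP 3.4 (Extent of Exposure) first gives a general definition: "Dose reduction for ibrutinib is defined as administered planned lower dose level". It then lists the levels by disease. For CLL/SLL: "There is a one applicable dose level reduction for CLL/SLL cohort: 280 mg/day (level 1 reduction"). For the other diseases there are "two applicable dose level reductions in FL, DLBCL or Richter syndrome disease cohorts: 420 mg/day (level 1 reduction") and 280 mg/day as level 2. The assigned starting dose is not mentioned. The requested outputs are the number of subjects with "any dose reduction (at least 1 reported dose reduction"), and the frequency and reason of reductions. Exposure is to be shown by disease type and by study cohort, and SAP 2.1 forms disease types from both parts of the study.

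Protocol 6.4.1, Table 7, is arranged by dose. Its columns are "Ibrutinib Dose | 420 mg | 560 mg" and its first step is "Dose Level -1 | 280 mg | 420 mg". The second step is not applicable from 420 mg and is 280 mg from 560 mg. The haematologic rows of Table 8 are also split by starting dose.

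Disease does not fix the starting dose in Part A. Table 4 assigns 420 mg to A1 and 560 mg to A2, and Protocol 4.1.1 admits to Part A, without tying disease to dose cohort: "Histologically confirmed and documented B-NHL (FL and DLBCL) or CLL/SLL". For Part B, Protocol 3.3.3 allows a lower dose chosen by the SET or this: "The highest planned dose (ibrutinib 560 mg daily + nivolumab 3 mg/kg every 2 weeks) in the dose optimization schedule". No disease-specific RP2D is stated.

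**The concern.** A reduction level has meaning only relative to where the subject started. The SAP uses disease as a stand-in for starting dose. That works only if every CLL/SLL subject starts at 420 mg and every FL, DLBCL and Richter subject at 560 mg. Part A does not require this: each dose cohort has one dose and may contain either disease group.

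At stake is how tolerability is described in the exposure tables. A programmer who follows SAP 3.4 literally would give some Part A subjects the wrong level or none. The disease-type tables would then put subjects with different starting doses under one label.

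**Working it through.** The plan gives no figure to reproduce, because this is a classification rule. The check applies both rules to every possible case.

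**Inputs**
- Protocol rule (Table 7): start 420 mg, 280 mg is level 1. Start 560 mg, 420 mg is level 1 and 280 mg is level 2.
- SAP rule (3.4): CLL/SLL, 280 mg is level 1. FL/DLBCL/Richter, 420 mg is level 1 and 280 mg is level 2.
- Current dose cannot exceed starting dose here; within-patient escalation is taken up under the fix. Each disease group then has 2 cases from 420 mg and 3 from 560 mg, so 2 × (2 + 3) = 10 combinations.

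| Disease group | Start (mg) | Current (mg) | Protocol level | SAP level | Agree? |
|---|---|---|---|---|---|
| CLL/SLL | 420 | 420 | none | none | yes |
| CLL/SLL | 420 | 280 | 1 | 1 | yes |
| CLL/SLL | 560 | 560 | none | none | yes |
| CLL/SLL | 560 | 420 | 1 | none | **no** |
| CLL/SLL | 560 | 280 | 2 | 1 | **no** |
| Other | 420 | 420 | none | 1 | **no** |
| Other | 420 | 280 | 1 | 2 | **no** |
| Other | 560 | 560 | none | none | yes |
| Other | 560 | 420 | 1 | 1 | yes |
| Other | 560 | 280 | 2 | 2 | yes |

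The rules agree in 6 of 10 combinations and disagree in 4. With levels keyed to starting dose, all 10 agree with the protocol.

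**How many subjects the mismatched rows could cover**
- Part A: Protocol 3.3.2 allows 6 to 9 subjects per dose cohort, and the disease mix is not given. The rows could cover 0 to 9 FL/DLBCL subjects in A1 and 0 to 9 CLL/SLL subjects in A2.
- Part B, if B1 starts at 420 mg and B2 to B4 at 560 mg: none.
- Part B, if all cohorts start at 560 mg: about 35 (B1).
- Part B, if all cohorts start at 420 mg: about 3 × 35 = 105 (B2 to B4).

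These are counts of subjects to whom a mismatched row could apply. They are not counts of mislabelled reductions, which also depend on how many of those subjects are reduced.

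**The case against.** The strongest defence is the SAP's own wording. A reduction must be to a lower level and must be reported. An A1 lymphoma subject who stays on the assigned 420 mg meets neither condition. So a reader might infer that such subjects will be counted as reduced, but the text does not establish this. What stands is narrower: the listed level 1 coincides with that subject's starting dose.

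A reader might likewise infer that a CLL/SLL reduction from 560 to 420 mg drops out of the any-reduction count. If it is reported, it can enter that count without a level. What stands is that the SAP lists no level for it. SAP 3.4 does not explicitly ask for a table by level, but it defines levels and ties the definition of a reduction to them, so the programmer has two rules that can conflict.

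The SAP's split also matches the monotherapy doses in Protocol 3.2 (420 mg for CLL/SLL; 560 mg for B-cell malignancies including FL and Richter syndrome). If Part B was dosed that way, its levels are correct. This does not help Part A.

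Finally, a reader might infer that an error in A1 and A2 could distort the choice of dose. The documents do not support that. The SET reviews DLTs, other safety data and PK after two cycles, guided by the mTPI table. An ibrutinib dose reduction is not among the DLT criteria in Protocol 3.3.1. The SAP's exposure summary belongs to an analysis run 6 months after the last subject's first dose, when Part B dosing was already settled. A1 and A2 are also shown separately by study cohort, and total dose and dose intensity do not use the levels.

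**Conclusion.** The mismatch is real and minor. As written, SAP 3.4 gives three wrong or missing level labels:
- CLL/SLL started at 560 mg: no level at 420 mg, and level 1 instead of 2 at 280 mg.
- Lymphoma started at 420 mg: level 2 instead of 1 at 280 mg.

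The fourth disagreement, a lymphoma subject remaining on an assigned 420 mg, is an ambiguity, because the reported-reduction wording may keep that subject out of the count.

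The Part A figures of 0 to 9 in each dose cohort are ranges, not estimates. Their upper ends need A1 to be all lymphoma and A2 all CLL/SLL. Through pooling, the same subjects enter the disease-type tables. The Part B effect may be zero and rests on starting doses that the documents do not state. Only descriptive exposure summaries are touched; RP2D selection, DLT evaluation and the efficacy analyses do not use these labels.

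**What to change.** In SAP 3.4, replace the disease-based list with a definition relative to each subject's assigned starting dose, reconciled with Protocol Table 7. Apply it both to whether a reduction occurred and to its level, and say whether the any-reduction count comes from reported reductions or from administered doses.

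Add a rule for Part A subjects escalated within-patient under Protocol 6.4.1. A subject who starts at 420 mg, goes to 560 mg and returns to 420 mg is below the escalated dose but not below the assigned start, so the SAP should say which reference applies.

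The cost is one or two SAP sentences and a small change to the derivation; no new data are needed. If the tables have already been produced, the A1 and A2 dosing records are the first to recheck, followed by any Part B cohort whose starting dose departed from the SAP's split. The change concerns labelling only and takes no view on any dose.

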| | Grade 2 | Persistent ^a ≤12 weeks: Continue study therapy; contact sponsor.. Persistent ^a >12 weeks: Discontinue study therapy |
| | Grade 3 | 1st event: Hold study therapy until resolution to Grade ≤ 1 
 Persistent^a ≤12 weeks: Resume at same dose Persistent^a >12 weeks: Discontinue study therapy 2nd event: discontinue study therapy |
| | Grade 4 or SAE of bleeding any grade | Discontinue study therapy |
| Lab values | Grade 1 | Continue study therapy and monitor in close intervals. |
| | Grade 2 | Persistent ^a ≤12 weeks: Continue study therapy. Persistent ^a >12 weeks: Discontinue study therapy |
| | Grade 3 | 1st event: Hold study therapy until resolution to baseline or Grade ≤1 
 Persistent^a ≤12 weeks: Resume at same dose Persistent^a >12 weeks: Discontinue study therapy 2nd event: Discontinue study therapy |
| | Grade 4 | Discontinue study therapy |
| | | |
| | | |
| Adverse Event | CTCAE Grade | Ibrutinib and Nivolumab * |
| Hematologic Toxicity | | |
| Neutropenia | Grade 1-3 | Continue study therapy; supportive therapy as per local/institutional guidelines |
| | Grade 4 | Supportive therapy as per local/institutional guidelines (hematology assessments twice weekly up to recovery). Any event not recovering to Grade ≤1 within 7 days (±2 days): discontinue study therapy. |

Table 8: Dose Adjustments for Related Non-hematologic and Related Hematologic Toxicities

| | | | | |
|----------------------------|------------------|---|-------------------------------|-------------------------------|
| | | For events recovering to Grade ≤ 1 within 7 days (± 2 days): | | |
| | | Toxicity Occurrence | Starting dose = 560 mg | Starting Dose = 420 mg |
| | | First | Restart at 560 mg | Restart at 420 mg |
| | | Second | Restart at 420 mg | Restart at 280 mg |
| | | Third | Restart at 280 mg | Discontinue study therapy |
| Febrile neutropenia | Grade 3 | Hold study therapy until resolution; supportive therapy as per local/institutional guidelines. Any event not recovering to \leq Grade 1 within 7 days: discontinue study therapy. For events recovering to Grade ≤ 1 within 7 days: | | |
| | | Toxicity Occurrence | Starting dose = 560 mg | Starting Dose = 420 mg |
| | | First | Restart at 560 mg | Restart at 420 mg |
| | | Second | Restart at 420 mg | Restart at 280 mg |
| | | Third | Restart at 280 mg | Discontinue study therapy |
| | | Grade 4 | Discontinue study therapy. | |

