| | Grade 2 | 
1st event: Hold until resolution to Grade ≤ 1.
 
 Improvement to \leq Grade 1: Resume study therapy at same dose and schedule. Worsening or persistence >3 days from day of onset despite oral steroid treatment: discontinue study therapy. 
2nd event: discontinue study therapy
 |
| | Grade 3 and 4 | Discontinue study therapy. |
| Renal/Creatinine | Section 8.5. (Table 14): Management of Renal Adverse Events | |
| | Grade 1 | Continue study therapy. |
| | Grade 2 and 3 | 
1st event: Hold until resolution to Grade ≤ 1.
 
 Improvement to \leq Grade 1: Resume study therapy at same dose and schedule. Worsening or persistence >7 days from day of onset: Discontinue study therapy. 
2nd event: discontinue study therapy
 |
| | Grade 4 | Discontinue study therapy. |
| Pneumonitis | Section 8.7. (Table 16): Management of Pulmonary Adverse Events | |
| | Grade 1 | 
Consider holding study therapy.
 
Improvement to baseline: resume dosing.
 
Worsening or persistence >7 days from day of onset: hold study therapy and treat as Grade 2.
 |
| | Grade 2 | 
Hold study therapy until resolution to Grade ≤ 1
 
Improvement to Grade ≤ 1 within 2 weeks: resume dosing.
 
Persistence for >2 weeks from day of onset: Discontinue study therapy.
 |
| | Grade 3 and 4 | Discontinue study therapy. |
| Hepatic alteration | Section 8.2. (Table 11): Management of Hepatic Adverse Events | |
| | Grade 1 | 
Continue study therapy.
 
Worsening or persistence >7 days from day of onset: hold study therapy and treat as Grade 2.
 |
| | Grade 2 | 
Hold study therapy until resolution to Grade ≤ 1.
 
Improvement to Grade ≤ 1 within 2 weeks: resume at same dose and schedule.
 
Persistence for >2 weeks from day of onset: Discontinue study therapy.
 |
| | Grade 3 and 4 | Discontinue study therapy. |
| AST/ALT and Bilirubin | Section 8.2. (Table 11): Management of Hepatic Adverse Events | |
| | Grade 1 | Continue study therapy. If worsens treat as Grade 3. |
| | Grade 2 | 
Consider hold study treatment until resolution to Grade ≤ 1
 
Persistent^a ≤ 12 weeks: Continue therapy at same dose and schedule.
 
Persistent^a >12 weeks: Discontinue study therapy
 |
| | Grade 3 and 4 | Discontinue study therapy |
| Recommendations for the management of immune-related adverse events and adverse events of clinical interest are provided in Section 8. | | |

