8.1. Gastrointestinal AE

Diarrhea and colitis have been observed in subjects receiving nivolumab. Early recognition and treatment of diarrhea and colitis are critical to their management. Subjects should be advised to seek immediate medical evaluation if they develop new-onset diarrhea, blood in stool, or severe abdominal pain or if they have worsening of baseline diarrhea. In subjects with pre-existing diverticulosis and/or diverticulitis receiving concomitant medication with corticosteroids, non-steroidal anti-inflammatory drugs (NSAIDs), and opioid analgesics together with nivolumab, diverticular perforation has been observed.

Table 10: Management of Immune-related Gastrointestinal Adverse Events

| Management and Follow-up of Immune-related Gastrointestinal Adverse Events. For dose modification guidelines, refer to Table 8 and Table 9. | |
|--|--|
| Grade 1 | Symptomatic treatment according to institutional standards Close monitoring; instruct subject to report worsening immediately and treat as Grade ≥ 2 |
| Grade 2 | ≤ 5 days: Symptomatic treatment according to institutional standards >5 days or recurrence: 0.5–1.0 mg/kg/d methylprednisolone.; consider prophylactic antibiotics; Persistence or worsening despite steroids >3 days: treat as Grade 3/4 Improvement to \leq Grade 1: taper steroids over at least 1 month, consider prophylactic antibiotics for opportunistic infections, resume study therapy per protocol |
| Grade 3-4 | Immediately: 1.0–2.0 mg/kg/d methylprednisolone IV; consider prophylactic antibiotics and lower endoscopy Persistence >3 days or recurrence: add infliximab 5 mg/kg (if no contraindication such as perforation or sepsis) Improvement to \leqGrade 2 within ≤ 3 days: taper steroids over at least 1 month |
| General | The oral corticosteroid equivalent of the recommended IV dose may be considered for ambulatory patients; the lower bioavailability of oral corticosteroids need to be considered. Clinical caution should be exercised, for subjects receiving concomitant medications of corticosteroids, NSAID, or opioid analgesics. In addition, be vigilant for signs and symptoms of potential perforation, especially in subjects with known diverticular disease. Narcotics should be used with caution as pain medicines may mask the signs of colonic perforation. |

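### Toxicity holds of ibrutinib shorter than 7 days that restart at the same dose are missing from the SAP's ibrutinib dose-modification summary

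*SAP*

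**What the plan says.** SAP 3.4 (Extent of Exposure) sets the threshold: "Dose interruption for ibrutinib is defined as missing/skipped dose for ≥ 7 day". It treats a run of consecutive missed days as one interruption, defines a reduction as administration of a planned lower dose level, and then says that "subjects with dose modifications (i.e., reductions or interruptions) and reasons for dose modifications will be summarized". For nivolumab, the same section counts a modification from one skipped dose, with no minimum duration.

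Three rows in Protocol 6.4.3 require a hold of study therapy, which Protocol 6.1 defines as both drugs and/or either one:

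- **Grade 3 febrile neutropenia (Table 8).** "Hold study therapy until resolution; supportive therapy as per local/institutional guidelines". If there is no recovery to Grade 1 or better within 7 days, therapy stops. After a first recovered event the subject restarts at the starting dose. Only from the second event does the dose fall ("Restart at 420 mg | Restart at 280 mg" for starting doses of 560 and 420 mg respectively).
- **Grade 2-3 renal events (Table 9).** The first event is held until Grade 1 or better and resumed at the same dose. "Worsening or persistence >7 days from day of onset: Discontinue study therapy".
- **Grade 2 enterocolitis or diarrhea (Table 9).** The first event is held and resumed at the same dose on improvement. "Worsening or persistence >3 days from day of onset despite oral steroid treatment: discontinue study therapy".

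For Grade 2 gastrointestinal events, Table 10 in Protocol 8.1 brings in steroids later: ">5 days or recurrence: 0.5–1.0 mg/kg/d methylprednisolone". Protocol 6.4.3 also says that treatment resumes at the next scheduled timepoint, without saying which timepoint applies to ibrutinib.

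**The concern.** The 7-day threshold lies at or above the point at which these rows, read as Tables 8 and 9 state them, have already ended the hold by restart or by discontinuation. A hold that the protocol required, that lasted 1 to 6 days and that ended in a same-dose restart therefore leaves no trace in the ibrutinib count of interruptions, in the count of dose modifications, or in the tabulated reasons.

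The safety profile of the combination is a secondary objective, and the modification summary is one of the places where a reader looks for tolerability. The two drugs are also counted by different rules. The SAP gives no reason for that, so their modification rates cannot be compared.

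**Working it through.** The documents state no rate or duration on this point, so there is no figure to reproduce. The check has two parts.

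**1. One record followed through the definitions.** Take a subject without run-in who has a first Grade 3 febrile neutropenia. Ibrutinib is held on Days 20-24 and restarted at the same dose on Day 25. The hold is 24 − 20 + 1 = 5 days. No lower dose is given, so there is no reduction; 5 < 7, so there is no interruption. The subject counts as having no ibrutinib modification.

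If the next scheduled timepoint means the next cycle Day 1, the restart is on Cycle 3 Day 1, which is Day 29. The hold is then Days 20-28, or 9 days, and it is counted. The restart rule alone decides the outcome.

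**2. Share of holds not counted.** Inputs are the SAP threshold (7 days), the limits D in Tables 8 and 9 (7 days for febrile neutropenia and renal events, 3 days for the gastrointestinal row) and the 14-day cycle. Days to recovery are assumed equally likely over 1 to D.

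- *Restart the day after recovery.* A hold is missed if it lasts 1-6 days, so the share missed is min(D, 6)/D.
- *Restart at the next cycle Day 1.* Let the hold start on cycle day s (1-14, equally likely) and recovery take d days. The hold is shorter than 7 days only if s ≥ 9 and d ≤ 15 − s. For D = 7 this gives 6+5+4+3+2+1 = 21 of 14 × 7 = 98 combinations. For D = 3 it gives 3+3+3+3+2+1 = 15 of 14 × 3 = 42.

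| Row | Limit D | Missed, restart next day | Missed, restart next Day 1 |
|---|---|---|---|
| Febrile neutropenia, renal | 7 days | 6/7 = 86% | 21/98 = 21% |
| Grade 2 GI, Table 9 limit | 3 days | 3/3 = 100% | 15/42 = 36% |
| Grade 2 GI, Table 10 timing (5 + 3 days) | 8 days | 6/8 = 75% | 21/112 = 19% |

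If febrile neutropenia and renal recoveries instead cluster evenly on days 5-7, with restart the next day, 2 of 3 (67%) are missed.

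**What the other outputs show.** A 6-day hold lowers ibrutinib dose intensity by 6/(2 × 30.4375) = 9.9% over 2 months and by 6/(15 × 30.4375) = 1.3% over 15 months, the range of median treatment duration expected in SAP 1.2. A 6-day hold covers a nivolumab Day 1 for 6 of 14 start days (43%). This is an upper bound on skipped infusions, since Protocol 6.3 allows an infusion up to 3 days after its scheduled date.

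**The case against.** A reader might infer that nearly all toxicity holds go unreported. The documents do not support that, for four reasons.

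- **No durations are given.** The 86% and 100% figures rest on uniform recovery times and on restart the day after recovery. The restart rule in Protocol 6.4.3 also allows a reading under which most of these holds are counted. A hold of exactly 7 days is counted on any reading.
- **The gastrointestinal limit is not simply 3 days.** It applies despite oral steroids, and Table 10 delays steroids, so such a hold could reach about 8 days.
- **Only some rows are affected in this way.** Grade 2 hepatic events and pneumonitis may be held for 2 weeks and general Grade 3 events for up to 12 weeks. Grade 4 thrombocytopenia has no time limit. Grade 4 neutropenia has no explicit hold instruction and a longer window: "Any event not recovering to Grade ≤1 within 7 days (±2 days): discontinue study therapy". Repeat febrile neutropenia that restarts does so at a lower dose and counts as a reduction.
- **Other outputs carry part of the information.** SAP 5.1 tabulates adverse events by action taken, with no 7-day threshold. Dose intensity falls with each missed dose, cycle delays and skipped infusions are counted, and holds that end in discontinuation appear in disposition.

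It is also fair that the SAP states its threshold openly, that the protocol sets no minimum length for a reportable interruption, and that no endpoint, test or dose-limiting toxicity determination depends on it.

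All of this stands, and it limits the size of the point. It does not remove it. Dose intensity gives neither a count nor a reason. The action-taken tables are organized by event, and if interruption is one of their categories they could show a held dose for a subject whom the exposure table lists as unmodified.

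**Conclusion.** The point holds in a limited form. Under SAP 3.4, a protocol-required ibrutinib hold of 1-6 days that restarts at the same dose is absent from the ibrutinib dose-modification summary and its reasons. This can happen under the first-occurrence febrile neutropenia, renal and Grade 2 gastrointestinal rows. It follows from the definitions alone and needs no assumption about durations beyond the possibility of such a hold.

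The share missed cannot be determined from the documents. With uniform recovery times and the limits in Tables 8 and 9, it lies between about 21% and 86-100%, depending on the restart rule. The Table 10 timing would put the gastrointestinal row at 19% or 75%. Under every reading computed, some required holds are missed. The effect is an undercount in one descriptive tolerability summary; the efficacy conclusions are untouched.

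**What to change.** In SAP 3.4, count any ibrutinib hold of at least 1 day with adverse event as the recorded reason as an interruption, and therefore as a dose modification. Tabulate these holds as 1-6 days and 7 days or more, so that the existing figure stays visible. Keep the 7-day threshold for doses missed for other reasons. This also brings ibrutinib closer to the nivolumab rule.

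The cost is SAP wording and one more table row. Protocol 6.1 and 6.2 already send dosing information and missed doses to the eCRF, and the SAP already plans to summarize reasons. The downside for the sponsor is a higher reported modification rate.

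Two timing passages should be reconciled so that hold length is defined in the same way at every site: which next scheduled timepoint in Protocol 6.4.3 applies to ibrutinib, and the Table 9 and Table 10 timing for Grade 2 gastrointestinal events. No view is taken here on which clinical rule is right.
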